5 STUDY EVALUATIONS AND MEASUREMENTS

5.1 Screening and Monitoring Evaluations and Measurements

5.1.1 Pre-operative Visit

5.1.1.1 Screening

- Potential subject is identified by the treating surgeon (match inclusion/exclusion criteria, surgical candidate)
- Complete informed consent/assent
- Review inclusion/exclusion criteria, complete inclusion/exclusion checklist
- Complete subject screening CRF

5.1.1.2 Pre-operative Medical Record/Radiograph Review

- Name
- Age
- Sex
- Race
- Ethnicity
- Date of birth
- MRN
- Diagnosis
- Clinical and surgical history (including history of pregnancy)
- Radiographic information and reports (including pre-operative coronal/sagittal; spine MRI)
- PFT data (if available)

5.1.1.3 Pre-operative Anesthesia Evaluation and Bloodwork (abstracted from medical record)

- Result of anesthesia evaluation: fitness for surgery, special notes
- Bloodwork results/levels

5.1.1.4 Pre-operative Physical Examination

- Standing height
- Weight

- BMI – (reported as %) as calculated by the medical record
- Trunk flexibility measurements (standardized): Adam's Forward bending test/inclinometer (degrees), thoracic and lumbar flexion (cm), thoracic and lumbar lateral flexion (cm)
- Data abstracted from clinical care exam (medical records, radiology reports, pulmonology tests)
- SRS 30 Questionnaire
- Clinical photographs

5.1.1.5 *Pre-operative Radiographs (abstracted from medical record)*

- AP/PA and lateral spine films
- Bone age hand radiograph (performed at physician discretion)
- Bending bolster films

5.1.2 *Surgical Intervention and Post-operative Course*

5.1.2.1 *Intra- and Post-operative Procedures*

- Anterior tethering surgery under general anesthesia with spinal cord monitoring
- Intraoperative fluoroscopy (<1 hour)
- AP/PA and lateral standing radiographs of the spine

5.1.2.2 *Intraoperative Data (abstracted from medical record)*

- Operative efficiency times (i.e. surgical start time, surgical end time)
- Intra-operative estimated blood loss
- Blood products utilized: cell saver (cc) given, other transfused blood products (cc)
- Number of portals
- Implant tracking Information:
 - Brand and model information of each implanted device
 - Part number, lot number, and UDI of staples, screws, locking caps, and PET cord
 - Type and size of screws used
- The extent of annulectomy (complete or partial) and the presence of pleural closure
- Whether a thoracoplasty was performed will be noted along with number of ribs and whether the pleura was cut or not (internal vs. external thoracoplasty – if used)
- Posterior based discectomy
- Antibiotic use
- Type and dose of antifibrinolytic
- Time-exposure of fluoroscopic x-ray during procedure

5.1.2.3 Post-surgical Data (abstracted from medical record)

- Chest tube drainage on day #1 - #5, and total collected
- Post-operative day of extubation as well as chest tube removal will be noted
- Post-operative day the patient was converted entirely to oral pain medication
- Visual Analogue Scores (measures the intensity of a child's pain experience) at discharge will be recorded. This is used to record the amount of back pain a patient is experiencing.
- Day of discharge will be recorded
- The use of a post-operative brace and the number of months utilized will be recorded
- Bloodwork levels and results from the hospital stay will be recorded
- Complications will be recorded: Complications will be recorded and status will be updated until resolved. This data collection methodology will be standardized via the complication form in the patient's study binder.
- Post-operative drain: type and drainage amounts daily until d/c of drain
- Data abstracted from medical records, radiology reports, and surgical logs
- Post-operative bloodwork

5.1.3 POD 21 Follow up

- Medical and radiographic record review: data abstracted from clinical care exam (medical records, radiology reports, pulmonology tests)
- Standing height
- Weight
- BMI

5.1.4 POD-45 and POD-90 Follow-up

5.1.4.1 Post-Operative Visit

- Medical and radiographic record review: data abstracted from clinical care exam (medical records, radiology reports, pulmonology tests)
- Standing height
- Weight
- BMI
- Trunk flexibility measurements (standardized): **Adam's Forward bending test (degrees) only**

5.1.5 POD-180, POD-365, POD-730 Follow-up

5.1.5.1 *Extended Follow-up Visit*

- Medical and radiographic record review: data abstracted from clinical care exam (medical records, radiology reports, pulmonology tests)
- Standing height
- Weight
- BMI
- Trunk flexibility measurements (standardized): Adam's Forward bending test (degrees), thoracic and lumbar flexion (cm), thoracic and lumbar lateral flexion (cm)
- SRS 30 Questionnaire
- Clinical photographs

5.1.6 Laboratory Evaluations

5.1.6.1 *Bloodwork*

Pre-operative bloodwork to be performed:

- CBC (Complete Blood Count) with(out) Differential
- CMP (Comprehensive Metabolic Panel) with(out) Albumin
- PT/INR (Prothrombin Time)
- PTT Profile (Partial Thromboplastin Profile)
- Type & Screen

These tests are performed pre- and post-operatively for all patients undergoing surgery, at clinical discretion. This is done as part of the anesthesia team's routine evaluation of the subject, and for tracking safe recovery. Results of these blood tests will be monitored for any abnormal or incidental findings. Abnormal or incidental findings will be documented and communicated to the treating physician(s). The treating physician(s) will determine if these findings would alter the subject's treatment course in any way.

5.1.6.2 *Pregnancy Testing: Performed at pre-operative visit only*

A blood or urine pregnancy test will be performed for female subjects 11 years of age and older, or any female who has begun menses will be required to complete a blood or urine sample pregnancy test. Results of such testing will be provided to the study participant, unless it is determined that she is unable to understand the significance or implications of a positive test result. In this case, the parent(s) will be informed of the positive result. In the event of pregnancy, the participant will not receive the study intervention. Participants who are found to be pregnant will be advised to contact family planning counseling services.

5.1.7 Other Evaluations, Measures

Clinical Evaluations/Measurements:

- Adam's Forward Bending Test: Subject stands with their back to the examiner, and bends forward at the waist, with knees in extension. The examiner looks at the horizontal plane of the spine, and measures the angle created between a rib hump and the horizontal plane. This is measured with an inclinometer.
- Thoracic/Lumbar Flexion Test: Subject stands with trunk erect while measuring tape is placed proximally on the spinous process of C7 and distally to S1. The subject then bends forward at the waist, with knees in extension. Following flexion of the vertebrae, using the same bony landmarks, the examiner calculates the difference in distance between the starting and ending positions.
- Thoracic/Lumbar Lateral Flexion Test: Subject stands erect with the feet flat on the floor. Place one end of a measuring tape on the tip of the middle finger and the other on the floor on a point directly beneath the middle finger. The patient then laterally flexes their trunk. The difference following the lateral flexion motion is measured.
- Clinical Photographs: Photographs will be taken of the subject at specified time points. The photographs will not include facial features, and include the torso from the top of the shoulders to the iliac crests. The patient should stand in a natural standing position for AP, PA, lateral right, and lateral left photos. The subject will perform the Adam's Forward Bending Test, and a photograph will be taken from the view of the examiner (PA). Photos will be taken without shirt or hospital gown. It is permissible for female subjects to wear a top covering that allows for a clear view of the spine and trunk (bra, sports bra, bathing suit top, or similar).

Other Measurements:

- Sanders Bone Age: Attached as Supplement 1
- SRS 30: Attached as Supplement 2

5.2 Safety Evaluation

Subject safety will be monitored by recording all AEs and SAEs, and will be recorded on the complication form in the patient's study binder. The evaluation of safety is a primary objective of this research study. There will be a clear classification of "device-related" adverse events. Device-related adverse events are those events directly related to the integrity, safety, or biomechanics of the Anterior Vertebral Tether Device, as described in this IDE application, comprised of the staples, screws, locking caps, and PET cord. This can include variables like device breakage or device migration. Other adverse events which are considered not device-related are those that are related to the act of surgery and medical recovery. The type of events will be documented on the CRF.

5.3 Efficacy Evaluation

This is a safety and feasibility clinical trial. A therapeutic exploratory endpoint for this VBT procedure will be measurement of the Cobb angle. The Cobb angle is a coronal plane radiographic measurement of curvature of the spine. This angle will be recorded for the pre-operative coronal spine radiograph, as well as all subsequent serial radiographs. The change

in Cobb angle (reduction) will be the primary exploratory therapeutic evaluator of efficacy. ‘Success’ of the intervention will be defined by a final Cobb angle of less than or maintained at less than 50 degrees, for curves which were less than 50 degrees pre-operatively. For curves which were greater than 50 degrees pre-operatively, a Cobb angle which is less than or maintained at less than 50 degrees is considered a ‘success’.

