	10. Investigator judgement that the subject/family may not be a candidate for the intervention
Number Of Subjects	The study will be conducted at The Children's Hospital of Philadelphia, Division of Orthopedics in up to 40 subjects. Subject inclusion will be based on interest of patients who present to the orthopedic clinic and satisfy the inclusion/exclusion criteria.
Study Duration	Each subject's active participation will last post-operatively and until approximately two years after skeletal maturity. The entire study is expected to last at least 10 years.
Study Phases: Screening	1. Screening phase: Subjects will be screened by study staff during a clinical visit in the orthopedics department. Eligible subjects will be approached and if interested, enrolled during a routine clinical exam.
Study Treatment	2. Study treatment: The subject will undergo surgical intervention using an accepted standard-of-care anterior approach using components from Globus Medical Inc. products, the Creo® Stabilization System, Transition™ Stabilization System, and SILC™ Fixation System . The investigational device is identified as the Anterior Vertebral Tether Device, comprising the staples, screws and locking

	caps from Creo® and the PET cord from the Transition™ Stabilization System and SILC™ Fixation System .
Post-op Follow-Up	3. Post-operative follow-up: Subjects will be followed at regular time points at 21, 45, and 90 days post-op during the post-operative phase. Patients will also be seen at visits 180, 365, and 730 days post-op during the extended follow-up phase. Long-term follow-up, beyond two years post-operatively, will occur through chart review of subjects, through two years beyond attaining skeletal maturity, which will be conducted under a separate study.
Efficacy Evaluations	The exploratory therapeutic efficacy evaluation measurement is thoracic Cobb angle (to nearest degree) at the pre-operative visit to Cobb angle during follow-up, especially at two years post-op (POD 730).

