Safety and Feasibility Evaluations	
We will use phase-specific endpoints to measure safety and feasibility:
 
 1) Study treatment phase: Any individual-level intraoperative events including neuromonitoring events (loss or change in neurological signaling or function), unanticipated events during surgery, and SAEs. 2) Post-operative active phase: Incidence of infection (within 90 days post-op), pneumothorax, bronchopulmonary plug, or any reportable SAE. 3) Extended follow-up phase: Incidence of over-correction, implant failure (measured on serial x-ray), incidence of curve progression to more than 50 degrees at two year follow-up, or incidence of secondary surgery or re-operation to correct further spine deformity (not related to trauma or other issues not related to the initial surgery/disease). Additional follow-up, through two years beyond skeletal maturation, will be conducted by periodic chart review. 4) Feasibility will be assessed by the capacity to successfully implant all components of the anterior vertebral tether device in subjects.
Statistical And Analytic Plan	The enrollment target of 40 subjects for this initial study of the device is based primarily on feasibility rather than statistical concerns. As such, analyses will be primarily descriptive for safety and feasibility. The Cobb angle, the exploratory therapeutic endpoint, will be evaluated as a continuous variable.
Data And Safety Monitoring Plan	The PI and Safety Officer will meet regularly to discuss any safety events. Safety Officer reports will be forwarded to the IRB during continuing review per CHOP Office of Research Compliance monitoring guidance. Safety reporting will be according to IRB

SOP 408 and governing FDA guidelines. The PI and study team will also comply with all CHOP Office of Research Compliance monitoring standards. The PI will meet with the study team regularly to discuss study progress and ensure data fidelity.

TABLE OF STUDY PROCEDURES

Study Phase	Pre-op / Screening	Surgery	Post-Operative Phase				Extended Follow-up Phase		
Visit Number	1	2	N/A	3	4	5	6	7	8
Study Days	Pre-op	0	1-44 (or until discharge)	21 (+/- 21 days)	45 (+/- 21 days)	90 (+/- 21 days)	180 (+/- 90 days)	365 (+/- 90 days)	730 (+/- 90 days)
Clinical Care (SOC) Evaluations:									
All procedures included here are standard-of care for a surgical orthopedic spine patient	X-ray: Hand Bone Age	*							
	X-ray: AP/PA and Lateral Spine	X		*	X	X	X	X	X

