4.7 Subject Completion/Withdrawal

Subjects may withdraw from the study at any time without prejudice to their care. They may also be discontinued from the study at the discretion of the Investigator for lack of adherence to study treatment or visit schedules, AEs, or due to non-compliance. However, in order to collect important study-related data for this investigational device, as much as is feasible, the Investigator and study team will make efforts to follow-up subjects who do not strictly adhere to timely visit schedules. The Investigator and study team may do this via emails, phone calls, or letters. The Investigator may also withdraw subjects who violate the study

plan, or to protect the subject for reasons of safety or for administrative reasons. It will be documented whether or not each subject completes the clinical study. If the Investigator becomes aware of any serious, related adverse events after the subject completes or withdraws from the study, they will be recorded in the source documents and on the CRF.

Subjects who are withdrawn from the study during the post-operative follow-up phases due to AEs/SAEs, such as tether failure or implant re-operation, will no longer be followed at study-specific visits. These subjects have the option to consent and allow for continued monitoring by medical and radiographic record review through the end of the two-year Extended Follow-up Phase. Subjects who are withdrawn from the study also have the option to enroll in a separate LTFU observational study.

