6.6.2 Stopping rules for SAEs that are device-related

Definition of Terms:

- Screw failure – screw, locking caps, and/or centering staple have loosened from the vertebra AND require re-operation.
- Tether failure – the tether has broken or lost tension. Diagnosed at any time point after 3 months by increased angulation at a disc space on standing PA radiograph or increase in disc wedging on side bending x-ray to the side away from the implant. Also, it is only an SAE if noted before maturity, overall Cobb angle worsens compared to the first erect measurement, AND requires re-operation.
- Implant re-operation - any problem with the implant that requires re-operation including re-operation for overcorrection with any of the following: a removal of all or part of the implant, loosening of the tension on the implant, or spinal fusion.

Stopping Rules

- Screw/locking cap/staple failure stopping point: 3 of first 5 cases, 5 of first 10, or in greater than 50% of cases 15 and beyond.
- Tether failure stopping point: 3 of first 5 cases, 5 of first 10, or greater than 50% of cases 15 and beyond.
- Implant failure re-operation stopping point: occurs in 3 of first 5, 5 of first 10, or greater than 50% of cases 15 and beyond.

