- Bronchopulmonary plug: After surgery, the patient will be monitored for presence of a bronchopulmonary plug by inpatient hospital staff. If a bronchopulmonary plug is found, it may cause elongation of the patient's hospital stay, or require a medical/surgical intervention.
- Implant Failure: We will diligently monitor the patient both during and after surgery for signs of implant failure. Some types of implant failure could be:

- Screw failure – screw and/or centering staple have loosened from the vertebra AND require re-operation.
- Tether failure – the tether has broken or lost tension. Diagnosed at any time point after 3 months by increased angulation at a disc space on standing PA or increase in disc wedging on side bending x-ray to the side away from the implant. Also, it is only an SAE if noted before maturity, overall Cobb worsens compared to the first erect measurement, AND requires re-operation.
- Implant re-operation - any problem with the implant that requires re-operation including re-operation for overcorrection with any of the following: a removal of all or part of the implant, loosening of the tension on the implant, or spinal fusion.
- Overcorrection: It is possible for the device to impart more than the intended correction to the spine curvature. This event will be monitored by consistent follow-up throughout the study, and may require medical or surgical intervention.

It should be noted that the above risks are the same risks that are present for standard-of-care surgery for spinal surgery. All appropriate clinical care procedures and pathways followed for standard-of-care spine surgeries will take place for these subjects.

9.3.2.2 No greater than minimal risk study procedures:

- Review of medical records: There is a risk of breach of confidentiality and privacy as a result of medical record review. This risk is minimized as detailed in Section 9.
- Administration of questionnaires: The questionnaires have the potential to make subjects feel uncomfortable. Subjects will be allowed to skip questions which they are not comfortable answering without compromising their participation in the study.
- Study-specific physical exam: The study physical exam uses non-invasive measurement techniques commonly employed in clinical practice.
- Clinical photographs: There is a risk of breach of confidentiality in subject photographs. This risk is minimized by not including the face of the subjects, and by the data protection plan in Section 9.

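### Section 5.3 scores exploratory success on Cobb angle alone, so a subject whose tether was re-operated or converted to fusion can count as a tether success

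*Combined protocol and SAP*

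**What the plan says.** Section 5.3 states that success of the intervention "will be defined by a final Cobb angle of less than or maintained at less than 50 degrees" where the curve was below 50 degrees before surgery. Where it was above 50, "a Cobb angle which is less than or maintained at less than 50 degrees is considered" a success. The same section has the angle recorded on the pre-operative film and on every later one.

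Section 6.3.3 makes Cobb change the exploratory endpoint, takes an intention-to-treat approach covering everyone who had the surgery, and plans a t-test and linear regression. The Synopsis treats the Cobb angle as continuous and points the comparison particularly at POD 730.

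Section 6.6.2 defines implant re-operation as "any problem with the implant that requires re-operation including re-operation for overcorrection", by any of "a removal of all or part of the implant, loosening of the tension on the implant, or spinal fusion". There it is a device-related term with its own stopping point. The Synopsis lists several extended follow-up outcomes: over-correction, implant failure, progression beyond 50 degrees at two years, "or incidence of secondary surgery or re-operation to correct further spine deformity".

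Under Section 4.7, subjects withdrawn during follow-up "due to AEs/SAEs, such as tether failure or implant re-operation, will no longer be followed at study-specific visits". Section 4.7.1 keeps the data collected up to withdrawal. Sections 4.7, 5.4 and 9.5 make later record and film review, up to two years, a matter of further optional consent.

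**The concern.** The success label is meant to describe what the tether did. As defined, it describes only the curve on some later film, whatever was done in between. A child whose tether was removed or who was converted to fusion is an implant re-operation in Section 6.6.2 and can be a success in Section 5.3. A film taken after fusion measures the fusion.

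The timing is also loose. One sentence of Section 5.3 says final without naming a visit. The other gives no time point. Neither covers a baseline of exactly 50 degrees. For a re-operated subject the final film could be the last one before re-operation, one taken after fusion, or none at all because the device failed and the subject left study visits. These choices give different success figures, and the plan does not choose between them. A reader who sees the separate re-operation count still cannot tell how those subjects entered the success and Cobb-change figures.

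**Working it through.** **1. The plan's own figure.** Section 6.4 states more than 80% power at n = 40 for a paired t-test at two-sided 5%.
- Thoracic: 17.9/6.6 = 2.71, exact power (noncentral t, 39 df) about 100%.
- Lumbar: 6.5/5.38 = 1.21, power above 99.99%.

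The statement holds as a lower bound. The documents give no success rate, tether re-operation rate or dropout rate, so steps 2 to 4 are illustrations.

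**2. Can a re-operated subject fall below 50 degrees?** The largest eligible curve is 60 degrees (Section 3.4.1).
- Correction needed: 1 − 50/60 = 16.7%. If the curve stands at 55, 65 or 70 degrees at re-operation: 9.1%, 23.1% or 28.6%.
- Section 1.3.1 quotes 57% correction for primary fusion. Applied to a conversion (an assumption), 60 × 0.43 = 25.8 degrees.
- For overcorrection no fusion figure is needed. Section 9.3.2 says "It is possible for the device to impart more than the intended correction to the spine curvature", so the angle would be expected to be below 50 already.

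**3. Success figure.** Let r be the number re-operated and m the number of other subjects at 50 degrees or more, with n = 40.
- Re-operation counted as failure: (40 − m − r)/40
- Re-operated subjects missing: (40 − m − r)/(40 − r)
- Cobb alone, all re-operated below 50: (40 − m)/40

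I take r = 2, 4 and 8. Section 1.3.1 quotes 4.6% to 19% long-term re-operation after fusion, which is 0.046 × 40 = 1.84 to 0.19 × 40 = 7.6 subjects. Using that range for a tether at two years is an assumption, as is m.

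| m | r | Re-operation = failure | Re-operated missing | Cobb alone |
|---|---|---|---|---|
| 2 | 2 | 36/40 = 90.0% | 36/38 = 94.7% | 38/40 = 95.0% |
| 2 | 4 | 34/40 = 85.0% | 34/36 = 94.4% | 38/40 = 95.0% |
| 2 | 8 | 30/40 = 75.0% | 30/32 = 93.8% | 38/40 = 95.0% |
| 0 | 4 | 36/40 = 90.0% | 36/36 = 100% | 40/40 = 100% |
| 4 | 4 | 32/40 = 80.0% | 32/36 = 88.9% | 36/40 = 90.0% |

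The gap between the first and last readings is r/40, or 2.5 points per re-operated subject below 50 degrees, whatever m is. If only half of the re-operated are below 50, the gap halves: for m = 2 and r = 4, 36/40 = 90.0% against 85.0%.

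**4. The planned t-test.** Section 6.4 gives no unit for 17.9 and 6.6; I read them as Cobb degrees (an assumption).
- Let 8 of 40 subjects show zero mean change. Mean = 0.8 × 17.9 = 14.32. Variance = 6.6² + (40/39) × 0.2 × 0.8 × 17.9² = 96.1, so SD = 9.81 and t = 14.32/(9.81/√40), about 9.2.
- With 4 such subjects: mean 16.11, SD 8.55, t about 11.9.
- In the flattering direction, suppose 4 re-operated subjects had 60-degree baselines and films after fusion at 25.8 degrees, a change of 34.2. The mean becomes (36 × 17.9 + 4 × 34.2)/40 = 19.5. The estimate moves by 1.6 degrees, and the conclusion that the angle changed is unaffected.

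**The case against.** The strongest reply is that the plan does imply a rule. Section 5.3 records the angle on all later films and Section 6.3.3 is intention to treat over everyone operated on, so later films count regardless of re-operation. That is a recognised strategy, with re-operation reported separately. A safety event and a controlled curve can also coexist in one child, so Sections 5.3 and 6.6.2 do not strictly contradict each other. Section 6 plans no analysis of a success proportion, the Synopsis treats Cobb as continuous, and withdrawal after re-operation is at the investigator's discretion.

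Most of this stands, and it limits the point. It does not remove it. If later films count regardless, the plan as written calls a converted subject a success of the tether. The strategy also needs the later films, and there is no analysis rule for when they are absent.

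A reader might infer more, and the documents do not support it:
- *That success and Cobb change are the trial's only statements on curve control.* The Synopsis also lists progression beyond 50 degrees at two years.
- *That re-operations are hidden.* They are a Synopsis outcome and have a stopping rule, and Grade III events are SAEs under Section 8.4.
- *That converted subjects would be moved to the fusion side of the Section 6.4 comparison.* The intervention received can naturally be read there as the index procedure, and nothing says otherwise.
- *That the original consent must be reopened.* The consent form was not available for this review, so its scope cannot be judged.

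**Conclusion.** The point holds and should be fixed, at a modest level. Followed as written, Section 5.3 can label a subject a tether success after implant re-operation, including fusion. It also leaves the final film, a baseline of exactly 50 degrees and missing POD 730 films without a rule.

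The size is 2.5 percentage points on the success figure for each re-operated subject below 50 degrees. With an assumed 4 re-operated and 2 other failures, success is 85.0% if re-operation is a failure and 95.0% on Cobb alone. The counts are assumptions, and the larger gap requires every re-operated subject to be below 50.

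The problem is confined to an exploratory label and to how the Cobb-change summary is read. It does not touch the primary safety endpoint, and the t-test conclusion would not change.

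**What to change.** - In Sections 5.3 and 6.3.3, define success as thoracic Cobb below 50 degrees at POD 730 (within the study's ± 90 days) without implant re-operation as defined in Section 6.6.2. Use all implanted subjects as the denominator, and one rule for every baseline, including exactly 50 degrees.
- If the Cobb-only label is kept, say that it ignores re-operation and report the composite beside it.
- For Cobb change, flag films taken after re-operation and show results with and without them. Add a worst-case sensitivity analysis for missing POD 730 films, with the worst-case value fixed in advance.

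The cost is protocol and SAP wording, a little more analysis, and a somewhat less favourable exploratory success figure. No new visits or films are needed.
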